**Faculty Mentor Name (if applicable):**

**A. SPECIFIC AIMS**

1) To determine the feasibility and acceptability of a pilot intervention addressing childhood sexual abuse among older adults living with HIV.

**B. BACKGROUND AND SIGNIFICANCE**

HIV/AIDS continues to be a major public health issue for older adults, locally, nationally and globally. In 2018, over half of people diagnosed with HIV were aged 50 and older (1). Around 1 in 6 new HIV diagnoses in 2018 were among people aged 50 and older (1) Based on data from the South Carolina Department of Health and Environmental Control and the Census, the case rate among adults 50 and older living in South Carolina was 521.1 cases per 100,000 population in 2016 (n=9,925 cases) and this population accounted for half of all people living with HIV (2). The prevalence of childhood sexual abuse (CSA) among older adults living with HIV may range from 16-22%. Older adults with CSA history had three to four times higher odds of reporting depression compared to older adults who did not experience CSA (3). Addressing CSA among older adults living with HIV (OALH) may help to reduce depression, which may help to improve ART adherence, viral suppression, and overall health-related quality of life (HRQoL).

**C. PRELIMINARY STUDIES**

This is Phase III of a 3-phase research project. The research team and PI have completed data collection for Phases I (qualitative study) and II (quantitative study) and are currently analyzing the data.

**D. RESEARCH DESIGN AND METHODS AND DATA ANALYSIS**

**Phase III (Pilot intervention):** A baseline assessment will be used to garner data on these relationships. ART adherence and viral suppression will be obtained by viral load data via assessment of medical record copies from recruitment sites, via informed and HIPPA consent. The data will then be deidentified and [name] will assist in the interpretation of viral load data to determine ART adherence and viral suppression of participants. HRQoL will be measured by the CDC Healthy Day Cores Module (HRQOL-4), (4) and CSA using 15 related items from the Early Trauma Inventory - Self Report (ETI-SR) (5). Concepts related to aging with HIV will include data on comorbidities using the Self-Administered Comorbidity Questionnaire (6); AIDS diagnosis using medical records; loneliness using the UCLA Loneliness Scale (7); HIV-

related stigma using the Berger Stigma Scale (8); and the role of caregivers in ART adherence. For potential mediators, coping strategies will be measured by the Brief Cope Scale (9); substance use using the Substance Abuse and Mental Illness Screener (10); and depressive symptoms using the 20-item Center for Epidemiologic Studies - Depression Scale (11). Data will also be collected on condomless sexual intercourse [vaginal, anal (receptive and/or insertive), oral] in the past 6 months (12); IPV victimization and/or perpetration using the Partner Violence Screen (13) and the Conflict Tactics Scale (14), respectively; and on sociodemographics including age, sex, race/ethnicity, education, income, sexual orientation, and time since diagnosis.

This phase is proposed so as to determine the feasibility and acceptability of the **Coping with Childhood Sexual abuse, HIV and Aging (CoSHA) intervention**. The CoSHA one-on-one intervention will be developed by drafting a manual, and having it reviewed by experts and potential users. Findings from Phase I will be the formative phase of providing input from the population for which the intervention will be designed. Input will also be sought from stakeholders (healthcare providers and ASO staff). Facilitators will be systematically trained using a criterion of successful implementation based on the REFLECT and the LIFT interventions. Implementation of treatment will be monitored to determine if the facilitator follows the approaches appropriately. CoSHA will be pilot-tested among OALH with CSA history and will use some of the main concepts from the REFLECT and LIFT interventions. Components to be used from REFLECT will include: appraisal and changeability of stressors related to aging with HIV; implementing adaptive problem- and emotion-focused coping skills; optimizing coping efforts by using interpersonal supports. Concepts from the LIFT intervention will include: identifying and expressing emotion related to CSA and perceptions of being a victim; identifying stressors and coping difficulties in relation to CSA; and developing adaptive strategies to reduce psychological stress. We will do theater/usability testing with 5 individuals to examine the preliminary intervention. Individual usability interviews with OALH will be conducted with the same recruitment procedures below. During the interviews, the moderator will walk the participant through each portion of the manual. Participants will be asked to reflect on whether the intervention met expectations. CoSHA will be a 5-session intervention with each session conducted weekly for five weeks. During the first session, baseline data will be collected and participants (N=40) will be randomly assigned to the intervention or to the 5-session attention control case management (ACCM) control group. For ACCM, participants will be given resources and will be able to talk about any issue of their interest. Sessions 2 and 3 for the intervention will focus on improving CSA coping strategies, and sessions 4 and 5 will focus on aging with HIV. Assessments will be done post session 5 (6-weeks post baseline), at 3 months, and at 6 months post baseline. A 3-month booster will be also given. After each session, the facilitator will complete quality assurance forms. The graduate research assistant or the PI will deliver the intervention.

Fidelity checks will be done by recording the sessions. Selected parts of the recordings of sessions will be reviewed and feedback will be provided to the facilitators. An

independent coder (undergraduate student) will estimate level of adherence to the CoSHA protocol. He/she/they will be trained to evaluate sessions using a checklist. Twenty percent (20%) of all recoded sessions will be coded to ensure the intervention is delivered as intended. Fidelity will be measured by calculating the percent performance of desired and undesirable behaviors during intervention delivery and will be done on a continual basis. If more focused training is required to improve fidelity, additional supervised sessions will be done until acceptable levels of fidelity are obtained.

**Location:** Recruitment will occur at the University of South Carolina Immunology clinic. After screening, and informed consent is obtained in person, data collection will be conducted in-person. Analysis will occur in the Department of Epidemiology and Biostatistics at the Arnold School of Public Health (ASPH). The five sessions will occur at the HIV clinic or in the Discovery Building at ASPH.

**Analytic approach.** Data collected will not be enough to perform advanced statistical analyses (N=40). Therefore, analyses will be for exploratory and informational purposes. For example, these data will inform on the length and burden of items asked. Evaluation of the intervention will occur throughout the pilot testing at each session, at post-intervention, and at three- and six-month follow-up.

The pilot study will be used to test recruitment methods, willingness of participants to participate, feasibility of the protocols, training staff, and examining data collection and retrieval methods. As a result, participants will be requested to evaluate each part of the intervention on the following criteria: suitability, impact, enjoyment, importance, interest, innovativeness, uniqueness, acceptability, and clarity. Participants will be asked to rate each portion on a 5-point Likert-type scale (e.g., 1 = very clear and 5 = not clear at all) as well as provide open-ended feedback. The goal is to assess the suitability, appropriateness, and tolerability of each component utilized. A modified version of the 8-item Abbreviated Acceptability Rating Profile (AAR) will be used to assess the intervention acceptability.

Participants will also be asked to evaluate the feasibility of recruitment methods and provide input on additional methods to be examined. As part of the evaluation of the study protocol and tasks, participants and facilitators will rate the extent to which the study protocol was presented in a logical, iterative, and cogent manner. Participants will also complete information about the facilitator and his/her training and professionalism. Having audiotapes of the sessions will also help to ensure the validity of protocol and serve as qualitative data for the evaluation of the project. Near the conclusion of the pilot, evaluation data will be analyzed and used to modify the intervention further for use in preparation of a R01 application to conduct a larger scale trial. Specifically, the outcome data will be analyzed using generalized estimating equations (GEE) in order to generate estimates of effect sizes for future large scale studies. It is important to note that once the intervention begins, no changes will be made to intervention materials for the pilot. Differences in feasibility and acceptability of the intervention by sex will also be noted.

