## **E. PROTECTION OF HUMAN SUBJECTS**

### **1. TARGET POPULATION:**

*Discuss the population you are targeting for the study (e.g., college students, elementary school students, adults with aphasia), the demographics of the population, any inclusion or exclusion criteria, and your anticipated sample size including method used to determine sample necessary to accomplish aims.*

**Inclusion/Exclusion criteria.** To be eligible, participants will be 50 years or older, HIV-positive, give informed and HIPAA consent to access medical records so as to obtain viral load measurements, not have significant cognitive impairment, <100% ART adherence in the past month, and score

Sample size: N=40. We will determine the feasibility and acceptability of the intervention, and preliminary efficacy.

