## 2. RECRUITMENT PLANS:

Advertisements will be placed in the waiting room at the immunology clinic. The clinic staff will inform the research staff of people who are 50 and older and then the research staff approaches these participants and determine their interest. If they are interested, we will determine eligibility in a private room. If eligible, we will obtain informed consent and HIPAA authorization. We have already obtained approval from the immunology clinic. Research staff will be at the clinic for recruitment.

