## 4. CONSENT/ASSENT:

*Describe procedures to be used to obtain consent/assent of subjects, including means that will be used to minimize any risks of coercion or undue influence.*

Research staff will obtain informed consent and HIPAA authorization. Potential participants will be informed about the study and we will garner their interest and eligibility before obtaining informed consent and HIPAA authorization. Participants will also be informed that they are free to leave the study at any time.

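### ART adherence is read from the same record viral load as viral suppression, so an adherence result would add no independent evidence; a graded past-month measure would fix this cheaply

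*Combined protocol and SAP*

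**What the plan says.** The measures paragraph of section D (Phase III, pilot intervention) states: "ART adherence and viral suppression will be obtained by viral load data via assessment of medical record copies from recruitment sites". It then assigns a team member to assist with "interpretation of viral load data to determine ART adherence and viral suppression of participants". The same paragraph names an instrument for quality of life, childhood sexual abuse, comorbidity, loneliness, stigma, coping, substance use, depressive symptoms and partner violence. For adherence, its only other entry is "the role of caregivers in ART adherence".

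Section E.1 (Target population) lists among the entry criteria "<100% ART adherence in the past month, and score", and the sentence breaks off there. On timing, section E.2 (Recruitment plans) says: "If they are interested, we will determine eligibility in a private room. If eligible, we will obtain informed consent and HIPAA authorization". Section E.4 (Consent/assent) agrees: "we will garner their interest and eligibility before obtaining informed consent and HIPAA authorization".

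On purpose, section A gives feasibility and acceptability as the only aim. Section E.1 adds: "We will determine the feasibility and acceptability of the intervention, and preliminary efficacy". The analytic part of section D says that "the outcome data will be analyzed using generalized estimating equations (GEE) in order to generate estimates of effect sizes for future large scale studies". Neither place lists the outcomes meant. Assessments follow at 6 weeks, 3 months and 6 months after baseline.

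**The concern.** Adherence and viral suppression appear as two variables, and section B speaks of them as two separate things that reduced depression might improve. Yet the plan obtains both by interpreting one laboratory value. Any adherence effect estimated this way restates the viral load data and cannot corroborate the suppression result.

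There is also a mismatch between selection and measurement. People enter because their past-month adherence is below 100%, so by that criterion every participant has room to improve. Viral load is a different concept: someone may miss doses and still have an undetectable value, and for that person a viral-load reading of adherence may leave little or no room for improvement.

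What is at stake is narrow: the preliminary efficacy statement and the effect sizes intended for the larger trial application. If adherence is among those outcomes, the next trial could be planned on two effect sizes that look like separate evidence but are not, or on an adherence effect that missed real gains.

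**Working it through.** **No stated figure to reproduce.** The sample size of 40 comes without alpha, power, effect size or dropout, and the point concerns how a variable is defined. The check is first a comparison of the text.

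1. *Source.* Section D says twice that both variables come from record viral load. It gives no cut-off, algorithm or date window that would separate them.
2. *Other adherence measures.* Section D lists none. The caregiver entry does not measure level of adherence. Section E.1 describes record access as serving viral load and mentions no refill data.
3. *Selection.* Section E.1 uses a percentage over a one-month period. Section D gives no rule for turning a viral load into such a percentage.
4. *Timing.* Sections E.2 and E.4 settle eligibility before HIPAA authorization, so the record viral load obtained under that authorization is probably not what screening uses.
5. *Repetition.* Nothing in section D says that the past-month measure is taken again at baseline or follow-up.

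**Illustration of overlap (all inputs assumed).** Suppose each variable is a single cut on the same viral load, with share pL below the lower cut and pH below the higher.

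- Participants classified differently = 40 × (pH − pL).
- Correlation phi = √[pL(1 − pH) / (pH(1 − pL))].
- Same cut: 0 of 40 differ, phi = 1.00.
- pL 0.50, pH 0.55: 40 × 0.05 = 2 differ; phi = √(0.225/0.275) = 0.90.
- pL 0.60, pH 0.80: 40 × 0.20 = 8 differ; phi = √(0.12/0.32) = 0.61.
- pL 0.70, pH 0.90: 40 × 0.20 = 8 differ; phi = √(0.07/0.27) = 0.51.

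**Illustration of the ceiling (all inputs assumed).** Let s be the share undetectable at entry and D = 0.30 the true between-arm difference in the proportion who improve. Suppose adherence is read from one current value against a detectability cut. Only improvement is counted; loss of suppression could still register.

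- Unable to show improvement = 40 × s: 40 × 0.5 = 20; 40 × 0.8 = 32.
- Visible difference if the effect is equal in both groups = (1 − s) × D: 0.5 × 0.30 = 0.15; 0.2 × 0.30 = 0.06.
- Smallest visible difference = 0, if all gains fall among the undetectable.
- Largest visible difference = min(D, 1 − s): 0.30 at s = 0.5; 0.20 at s = 0.8.

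The visible part of a true 30-point difference is thus anywhere from 0 to 30 points at s = 0.5 and from 0 to 20 at s = 0.8. These ranges show what is possible; they do not estimate what will happen.

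**The case against.** The strongest reply is that adherence is nowhere listed as an outcome. The sole aim is feasibility and acceptability, section D describes the analyses as exploratory, and its measures paragraph opens by speaking of a baseline assessment. Section B offers adherence as rationale, not as an endpoint. This stands: a reader might infer that the trial has an adherence outcome lacking a valid measure, but the documents do not say that adherence is an outcome, so the point is conditional.

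Three other strong readings also go too far.

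- *That the plan fails to name its screening measure.* The eligibility sentence breaks off. The readable criteria contain no childhood sexual abuse requirement, although section D pilots the intervention in people with that history, so criteria text has probably been lost. A tool named there cannot be excluded, and the break is not an error in the plan.
- *That screening must use a different measure.* Section E.1 makes HIPAA consent itself an entry criterion, so the sequence is not perfectly clean. A separate measure remains the likelier reading, given sections E.2 and E.4.
- *That participants who enter undetectable cannot improve.* This assumes one value against a detectability cut. Section E.1 refers to measurements in the plural, and section D leaves interpretation to a team member, so serial values may be used. The supportable statement is that they may not be able to show improvement.

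It is also fair to say that an objective marker is a defensible choice in a 40-person pilot, and that self-report has its own weaknesses. That bears on the choice of fix. It does not make two readings of one viral load into separate evidence.

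**Conclusion.** The point holds as a cheap improvement, with moderate confidence. As written, adherence gives no evidence independent of viral load, and the plan selects participants on a different concept of adherence that section D does not carry forward. The feasibility and acceptability aim is unaffected.

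The consequence depends on adherence being among the outcomes behind preliminary efficacy or the GEE effect sizes, which is not stated. If it is, its effect size would not be separate from that for suppression, and gains among participants who enter undetectable may go unseen. It would be too strong to call the two variables identical: how far they overlap depends on an interpretation rule that the plan does not give. The size cannot be derived from the documents; every input to the overlap and ceiling illustrations is an assumption.

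**What to change.** In the measures paragraph of section D, delete the words *ART adherence and* from both sentences on viral load, so that record viral load serves viral suppression only.

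Measure ART adherence with a named, graded past-month measure, recorded as a percentage, at baseline, 6 weeks, 3 months and 6 months, and compare it between arms. A yes/no item would not do: everyone enters below 100%, so all baselines would be equal and partial gains would be invisible. If no such measure is added, do not report adherence as an outcome separate from viral suppression; that option costs wording only.

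Costs and downsides of adding the measure:

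- A few extra items at assessments that already take place; section D already plans to look at item burden.
- Self-report error, if the measure is self-reported. It may differ by arm because participants know which sessions they receive, and the between-arm comparison does not remove this. Viral suppression remains as the objective companion measure.
- Regression to the mean, because entry requires adherence below 100%. The between-arm comparison addresses this; within-arm change should not be read as an effect.

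No viral load data are lost.

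### The pilot is meant to test recruitment methods and willingness to take part, but the only recruitment evaluation specified is participants' opinion, with no counts at approach, interest, eligibility or consent

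*Combined protocol and SAP*

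**What the plan says.** Section D, under Analytic approach, states what the pilot is for: "The pilot study will be used to test recruitment methods, willingness of participants to participate, feasibility of the protocols". Later in the same section comes the one evaluation directed at recruitment: "Participants will also be asked to evaluate the feasibility of recruitment methods and provide input on additional methods to be examined".

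Section E.2 describes how people enter. Advertisements hang in the clinic waiting room. Clinic staff also point out patients aged 50 and older, after which "research staff approaches these participants and determine their interest. If they are interested, we will determine eligibility in a private room". Consent and HIPAA authorization follow for those found eligible. Section E.4 confirms the order: "we will garner their interest and eligibility before obtaining informed consent and HIPAA authorization". Section D adds five usability interviews recruited by the same route: "Individual usability interviews with OALH will be conducted with the same recruitment procedures below".

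Neither E.2 nor E.4 specifies a log, a count or a rate at any step. The only recruitment number is the enrolment target of 40 in section E.1.

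**The concern.** Willingness to take part is a proportion: those who agree, out of those asked. The stated method questions a group in which everyone agreed. Their opinions may show how recruitment felt to people for whom it worked. They cannot show how often it failed, or at which step.

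The order of steps makes this sharper. Interest is asked before eligibility, so a person who declines at first contact is never screened. Even a consent rate among eligible people would leave that person out.

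At stake is the planning of the larger trial for which section D says the pilot prepares. That trial will need to know how many patients must be approached per person enrolled. If refusals are not recorded when they happen, the figure cannot be rebuilt afterwards.

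**Working it through.** **No plan figure to reproduce.** The documents state no recruitment, eligibility or consent rate, and the target of 40 comes without a derivation. The check is therefore a reading of the whole document for a count at each step, followed by an illustration.

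**Step 1: what is specified at each step.**

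| Step | Where described | Count specified? |
|---|---|---|
| Advertisement | E.2 | No |
| Approach by research staff | E.2 | No |
| Interest | E.2, E.4 | No |
| Eligibility | E.2, E.4 | No |
| Consent | E.2, E.4 | No |
| Enrolment | E.1 | Target of 40 only |

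The other evaluation tools in section D (component ratings, the acceptability scale, ratings of protocol and facilitator, audio recordings, fidelity coding) concern the intervention and its delivery. None describes collecting anything from people who decline.

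**Step 2: which rates follow from the specified data.** Three proportions describe recruitment: interested/approached, eligible/screened and consented/eligible. Only the number enrolled is sure to be known, so none of the three can be calculated from what is specified.

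**Step 3: illustration (all counts assumed).** Take two clinics, each with 225 interested and screened, 45 eligible and 40 consenting. They differ only in the number approached. Exact (Clopper-Pearson) 95% limits for x out of n are the 0.025 quantile of Beta(x, n−x+1) and the 0.975 quantile of Beta(x+1, n−x).

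| Proportion | Clinic A | Clinic B |
|---|---|---|
| Interested/approached | 225/250 = 90.0% (85.6–93.4) | 225/750 = 30.0% (26.7–33.4) |
| Eligible/screened | 45/225 = 20.0% (15.0–25.8) | the same |
| Consented/eligible | 40/45 = 88.9% (75.9–96.3) | the same |

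The same 40 people would give the same opinions in both clinics. Only a count that starts at first approach tells A from B. The example shows that a ratio needs its denominator; it says nothing about what this clinic's rates will be.

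**Step 4: rough size of the group not counted.** Section B gives a prevalence of childhood sexual abuse (CSA) of 16–22% in older adults living with HIV, and section D says the pilot is for people with that history. On this criterion alone, the number to screen is 40/0.22 = 181.8, so 182, up to 40/0.16 = 250. That leaves 182 − 40 = 142 to 250 − 40 = 210 people screened but not enrolled. This assumes that the prevalence applies at this clinic, ignores the other eligibility criteria, and takes everyone found eligible to consent. People who decline before screening come on top.

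**The case against.** Five things can be said for the plan.

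- **The word participants is used loosely.** Section E.2 uses it for people only being approached, so the opinion question could in principle reach people who did not enrol. This ambiguity is real. But elsewhere in Analytic approach the word means people who rate the intervention and the facilitator, which points to those enrolled.
- **Willingness may mean willingness to keep attending.** Attendance at sessions and assessments can be counted from the schedule and the payments in section E.8. On that reading the plan is not silent on willingness. It still says that recruitment methods will be tested, and for that it offers only opinion.
- **A log may exist in practice.** Research staff will be at the clinic and will handle interest and eligibility person by person. In a short form of this kind, silence does not show that no record is kept. This stands: the supported statement is that no count is specified.
- **The pilot is declared exploratory.** That explains why no formal testing is planned. Counting needs no power, and it serves a purpose that the plan itself names.
- **The numbers above are weak evidence of size.** This also stands. The funnels are invented, and the 20% yield was chosen, so its lying within 16–22% confirms nothing.

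A reader might also infer that the single specific aim goes unmeasured, or that the planned sex comparison fails for lack of these counts. The documents do not support either. Section A speaks of the feasibility and acceptability of the intervention, and the sex comparison is worded the same way: "Differences in feasibility and acceptability of the intervention by sex will also be noted". Feasibility of delivery does have a measure: "Fidelity will be measured by calculating the percent performance of desired and undesirable behaviors during intervention delivery". Recruitment is a further use of the pilot, named only under Analytic approach.

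**Conclusion.** The concern holds for recruitment, and for willingness in the sense of agreeing to join. The plan names both as things to be tested, then specifies only an opinion question to a group most naturally read as those who agreed. As written, it yields no willingness at first contact, no screening yield and no consent rate.

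It would go too far to conclude that these data will not exist, since the documents neither provide for a log nor exclude one. Nor is the pilot invalid: its measures of delivery and acceptability are untouched. The size of the gap cannot be taken from the documents. The 90% against 30% contrast is illustrative only, and the figure of 182 to 250 screened rests on the assumptions stated with it. The change should be made because it is cheap before recruitment and because unlogged refusals are lost for good.

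**What to change.** **In section E.2,** specify a de-identified tally, within ethics approval, that starts at first approach and counts people approached, interested, screened, eligible, consented and randomised. Count two groups separately: people who respond to the advertisement, because the number who saw it is unknown and they have no approached denominator; and recruits for the five usability interviews, who come by the same route for a different purpose.

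**In Analytic approach,** name as the recruitment feasibility measures, each with an exact 95% confidence interval:

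- interested/approached (willingness at first contact);
- eligible/screened (screening yield);
- consented/eligible (consent rate).

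Keep participants' opinions of the recruitment methods as supporting data, and say whether people who decline are to be asked.

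**Cost.** The work is a tally sheet for research staff who will already be at the clinic. The downsides are that small logging task, a possible ethics review because the tally covers people who have not consented, and recruitment figures that may look less favourable than opinions from enrolled people. If a log is already planned, the change is a few sentences of text.
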